e. It is recommended that the **CCI** (**CCI**)) are completed by the subject before he is seen by the physician for interview and before other (trial specific) assessments are performed, as well as before the administration of IMP, in order for the answers not to be influenced by the information given by the physician, by the administration of IMP, or by early side-effects of the IMP or (trial related) assessments. During the screening visit, the **CCI** are completed after ICF signature, but before other (trial specific) assessments are performed. At each visit, the questionnaires are to be completed in the same order every time, following the order presented in the protocol. The questionnaires are to be completed under site supervision at the site. For those subjects where the Month 24, Month 36, Month 48, and/or Month 60 visits are impacted by COVID-19, the questionnaires may be conducted at the site within the following window: up to -1 month prior to the target visit, up to +2 months after the target visit, and at least 4 months after the last assessment. Adjustments to the visit timing within this window are to be documented.

- f. For those subjects where Month 30, Month 36, Month 42, Month 48, Month 54, and/or Month 60 visits are impacted by COVID-19, abdominal ultrasounds may be conducted within the following window: up to -1 month prior to the target visit and up to +1 month after the target visit. Adjustments to the visit timing within this window are to be documented.
- g. After week 52, the visit frequency is every 26 weeks (6 months). In this long-term follow-up phase there should be at least quarterly contact between the site staff and subject to monitor the occurrence of adverse events.

Version: 4.0 (Amendment 3.0)

AMT-061 (AAV5-hFIXco-Padua; etranacogene dezaparvovec) Protocol ID: CT-AMT-061-01

Table 4 Flow Chart for Laboratory Parameters, for Long-Term Follow-up (up to Month 60)

Trial Period	Long-Term Follow-up											
Months	18 ^{b, c}	24 ^{b, c}	30 ^{b, c}	36 ^{b, c}	42 ^{b, c}	48 bb, c	54 ^{b, c}	60 ^{b, c}				
Visit Window (Weeks)	±2	±2	±2	±2	±2	±2	±2	±2				
Local Laboratory												
Factor IX: one-stage aPTT for factor IX activity for local monitoring			x	x	X	x	x	X	(x) ^a			
Transaminases (AST/ ALT) for local monitoring ^d			X	x	X	X	x	X	(x) ^a			
Central Laboratory												
One-stage aPTT for factor IX activity	х	х	Х	Х	Х	Х	Х	х	(x) ^a			
Chromogenic assay for factor IX activity ^e	Х	х	х	х	х	х	х	х	(x) ^a			
Factor IX protein concentration	х	х	Х	х	Х	Х	х	х	(X) ^a			
Anti-factor IX antibodies		х		Х		Х		х	(X) ^a			
Factor IX inhibitors (Nijmegen modified Bethesda assay) ^f		х		х		х		X	(x) ^a			
factor IX Recovery ^g									(X) ^a			
Total (IgM and IgG) antibodies to AAV5		х		х		х		X	(x) ^a			
Neutralizing antibodies to AAV5		х		х		Х		Х	(x) ^a			
Sampling for vector genome detection: - Blood ^h	Х	х	x	x	x	x	x	х	(X) ^a			
- Semen ^h	х	х	х	х	х	х	х	х	(x) ^a			
Alpha-fetoprotein	Х	Х	Х	Х	Х	Х	Х	Х	(x) ^a			
Hematology and coagulation parameters ⁱ	Х	Х	х	х	х	х	x	Х	(X) ^a			
Serum chemistry parameters ^j	х	х	Х	х	Х	Х	х	Х	(X) ^a			

AAV5: adeno-associated viral vector serotype 5; ALT: alanine aminotransferase; aPTT: activated partial thromboplastin time; AST: aspartate aminotransferase; IgG: immunoglobulin G; IgM: immunoglobulin M; IMP: investigational medicinal product.

a. An additional visit can be performed at any time for the purpose of conduct of one or more procedures listed in the column "Additional Visits" according to the choice of the Investigator. Hence, "(x)" refers to a procedure that can be performed, if judged relevant by the Investigator.

b. Each visit and time point is scheduled in relation to date of IMP administration, not in relation to the date of its previous visit or time point.

c. For subjects on routine prophylactic factor IX replacement therapy, these visits should take place on the day that routine prophylactic factor IX replacement treatment is planned to be administered. At these visits, blood sampling will then take place prior to administration of prophylactic factor IX replacement therapy. If a subject uses additional on-demand factor IX replacement treatment, his upcoming study visit may need to be re-scheduled (to the extent the visit window allows) so that the visit takes place at the time the subject resumes his routine prophylaxis schedule. For subjects only using on-demand factor IX replacement therapy (only applicable after AMT-061

AMT-061 (AAV5-hFIXco-Padua; etranacogene dezaparvovec)

Protocol ID: CT-AMT-061-01

administration), his upcoming study visit may need to be re-scheduled (to the extent the visit window allows) so that the visit does not take place within 10 days of any ondemand factor IX product use.

- d. For ALT level increments of at least 2-fold baseline (i.e., pre-IMP) and/or > upper limit of normal (ULN), by local or central laboratory, the Investigator should contact the Medpace and uniQure Medical Directors to discuss a clinical management plan, on a case-by-case basis, including potential re-tests and/or initiation of corticosteroid treatment. In case of AST level increments > ULN, the Investigator should contact the Medpace and uniQure Medical Directors and a similar discussion should take place.
- e. No additional blood will be drawn for the chromogenic assay; the test will be performed on backup samples.
- f. In case of a positive test for factor IX inhibitors, a re-test should be performed with two weeks to confirm the positive test. The subject should be called in for an additional visit in case no routine visit is scheduled within this two-week timeframe.
- g. At suspicion of factor IX inhibitor, the factor IX recovery assessment should be repeated. Blood samples for factor IX recovery assessment should be drawn just prior to administering the factor IX challenge dose (40 U/kg) and at 30 minutes after the factor IX challenge dose is administered.
- h. Sampling for the individual subject and for a specific matrix (i.e., blood or semen) is only to be continued until 3 consecutive negative samples have been detected for the subject for that particular type of matrix. The sampling schedule (frequency) may be increased as agreed between the Investigator and subject following the notification of a first negative result on blood and/or semen, expediting the opportunity to reach three consecutive negative samples on the specific matrix. Based on the wish of the subject, semen samples can be collected at home prior to attending the visit (at the visit day or at the day before the visit day). Also, the frequency of semen sampling may be reduced (to be agreed between Investigator and subject) as long as the subject uses a condom during sexual intercourse until 3 consecutive negative samples have been detected. Semen samples are only to be collected as applicable.
- i. For hematology: hemoglobin, hematocrit, platelet count, red blood cells, white blood cells with differential count (all expressed in % as well as in absolute numbers); for coagulation: aPTT and prothrombin time (or INR [International Normalized Ratio]).
- j. Serum electrolytes (sodium, potassium), creatinine, creatine kinase, gamma-glutamyltransferase (γ GT), aspartate aminotransferase (AST), alanine transaminase (ALT), alkaline phosphatase (ALP), C-Reactive Protein (CRP), albumin, total bilirubin, glucose (non-fasting).

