6.1.2 IMP Administration

The day of IMP administration should be planned to take place as an overnight stay at the clinic and should take place within a maximum of six weeks after the Screening visit (unless sponsor approved a prolonged screening period as described in Section 6.1.1).

The baseline visit should also be planned as such that the baseline blood sample for factor IX activity and factor IX protein concentration assessment will be drawn at the point in time where factor IX activity and factor IX protein concentration is expected to be closest to trough levels (i.e., the baseline visit should be scheduled on days when routine factor IX prophylaxis is due to be administered). In case of on-demand factor IX replacement therapy use in proximity to the scheduled visit, the exogenous factor IX is to be washed out and the visit is to be rescheduled to the extent the visit window allows. The wash out period will be minimal 10 days for short-acting factor IX or more for long-acting factor IX (depending on half-life).

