6.2.2.3 Factor IX Activity Levels and Factor IX Protein Concentration

Blood samples for determination of endogenous factor IX activity and factor IX protein will be collected and assessed at the central and/or local laboratory as indicated in the flow chart (Table 2). Central laboratory results for factor IX activity will be used in the analyses and local laboratory results for factor IX activity will be used for local monitoring of subjects.

Throughout the study, it will be the aim to draw blood samples at those time points when the subject's factor IX activity is expected to be at its trough.

For subjects on routine prophylactic factor IX replacement therapy:

- The Investigator and/or study nurse will collaborate with the subject to schedule study visits to take place on days when continuous routine prophylactic factor IX replacement treatment is due to be administered. At these visits, blood sampling will then take place just prior to administration of prophylactic factor IX replacement therapy at the clinic.
- If a subject uses additional on-demand factor IX replacement treatment, his upcoming study visit may need to be re-scheduled (to the extent the visit window allows) so that the visit takes place at the time the subject resumes his routine prophylaxis schedule.

For subjects only using on-demand factor IX replacement therapy (only applicable after AMT-061 administration):

• If a subject uses on-demand factor IX replacement treatment, his upcoming study visit may need to be re-scheduled (to the extent the visit window allows) so that the visit does not take place within 10 days of any on-demand factor IX product use.

Factor IX activity will be assessed by using the one-stage aPTT assay and a chromogenic assay (central laboratory). No additional blood will be drawn for chromogenic assays of factor IX activity; the test will be performed on back-up samples.

AMT-061 (AAV5-hFIXco-Padua; etranacogene dezaparvovec) Protocol ID: CT-AMT-061-01

CCI
CCI
CCI

AMT-061 (AAV5-hFIXco-Padua; etranacogene dezaparvovec) Protocol ID: CT-AMT-061-01

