- An unplanned assessment will be assigned to a scheduled visit only if that visit has a missing value for the relevant endpoint and the visit was a scheduled time point for the performance of the assessment per the study protocol.
- Analysis windows for the assignment of unplanned assessments will range from the previous visit at which the endpoint is planned to be collected to the next visit at which the endpoint is planned to be collected.
- The unplanned assessment closest in time within the analysis window (either before or after) will be used to replace a missing assessment for a scheduled visit. If two unplanned

assessments are both the closest in time, with one being before and the other being after, the earlier assessment will be used.

- For visit-based efficacy endpoints, values obtained before the post prophylaxis period will not be candidates to be used for imputing missing values for post-treatment visits that are during the post prophylaxis period.
- For all visit-based endpoints, values obtained prior to treatment will not be used for imputing missing values for post-treatment-period planned assessments.
- Only values from unplanned assessments (not planned assessments) will be used to replace a missing scheduled assessment.
- An unplanned assessment may be used more than once provided it lie within the analysis window for two consecutive scheduled time points at which the assessment was not performed as planned.

For factor IX activity and factor IX protein, only central-laboratory unplanned-assessment values will be candidates for assignment to a scheduled visit that has no central-laboratory value.

An exception to the above windowing rules is that Vital Signs will have values assigned to analysis visits according to the visit windows given in Table 6 (Analysis Study Time Windows for Vital Signs Assessments).

Any other rules for missing data handling will be given in the endpoint-specific sections.

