For the Week 6 and 52-Week data-cut analyses, the contamination rule, as stated above, was 10 (discrete) days. Specifically - Factor IX activity levels during the period of use or within 10 days after the end of use of exogenous factor IX replacement therapy were not included in these analyses; the last (calendar) day of use and the subsequent nine (calendar) days are considered to be contaminated. Beginning with the 2.5-year (data cut) analysis, the contamination rule is hereby refined as follows. Factor IX assessments post-AMT-061 that are within 5 half-lives of exogenous factor IX use are considered contaminated and will be excluded from the analysis. Going forward, this 5-half-life contamination rule replaces the 10-day contamination rule. Both the date and time of the exogenous factor IX infusion start and the blood sampling for factor IX activity assessment will be taken into account to determine whether there was contamination. If the factor IX activity assessment was performed prior to the infusion start time, then the assessment is not considered to be contaminated by that infusion. See further detail in the [Data Handling Rules Appendix](#) in this document [under the category of “Contamination due to exogenous factor IX (infusion) use”].

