6.9 Statistical Analyses for the Month 60 CSR Addendum

The same analyses that are to be done for the Week 52 main CSR (and the 2.5 year CSR) – as described in [Sections 6.3, 6.4, 6.5, 6.6, 6.7, and 6.8](#) – will be repeated for the Month 60 CSR, but using the entire 60 months (instead of 52 Weeks [or 2.5 years]) of data.

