7. CHANGES FROM METHODS PLANNED IN THE PROTOCOL

Beginning with the 2.5-year (data cut) analysis, the contamination rule (for factor IX activity analysis) is hereby refined as follows. Factor IX activity assessments post-AMT-061 that are within 5 half-lives of exogenous factor IX use are considered contaminated and will be excluded from the analysis. Going forward, this 5-half-life contamination rule replaces the 10-day contamination rule. The rationale is to improve accuracy. By contrast, the protocol currently states the following: “The required wash out period (in order to consider a factor IX activity level to be “unaffected” – i.e., “uncontaminated”) will be 10 days.”.

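### Long-term visits are timed to a flat 10 days after on-demand factor IX, but the SAP excludes values within 5 half-lives, so a compliant visit can yield an excluded value

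*Protocol*

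**What the plan says.** **Visit timing.** Table 4 footnote c covers subjects who use factor IX only on demand after AMT-061. Their visit may need to be moved, within the window, "so that the visit does not take place within 10 days of any ondemand factor IX product use". Protocol 6.2.2.3 repeats the 10 days in the body text ("If a subject uses on-demand factor IX replacement treatment, his upcoming study visit" may need to be rescheduled). Neither place distinguishes products. The long-term visit window is ±2 weeks.

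**Analysis.** SAP 6.7.1, from the 2.5-year data cut: "Factor IX assessments post-AMT-061 that are within 5 half-lives of exogenous factor IX use are considered contaminated and will be excluded from the analysis". SAP section 7 declares this as a departure from the protocol: "Going forward, this 5-half-life contamination rule replaces the 10-day contamination rule". SAP 6.9 carries it to the end of the trial, because the same analyses "will be repeated for the Month 60 CSR".

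**What did not change.** SAP section 7 speaks only of the analysis. Protocol Version 4.0 (08 Feb 2022) is later than the SAP table shells (16 Jun 2021), yet it keeps 10 days in Table 4, in 6.2.2.3 and in the statistical text of 9.9.1.

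**The protocol's own view of long-acting product.** For the baseline visit only, Protocol 6.1.2 says: "The wash out period will be minimal 10 days for short-acting factor IX or more for long-acting factor IX (depending on half-life").

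**Filling gaps.** SAP 6.3 lets an unplanned central-laboratory factor IX value stand in for a missing scheduled one, but not a neighbouring planned visit: "Only values from unplanned assessments (not planned assessments) will be used to replace a missing scheduled assessment".

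**The concern.** The rule that decides when a sample is drawn should be at least as strict as the rule that decides whether the sample is used. Here it is not, once the product has a long enough half-life. A site can follow the footnote exactly and still produce a value that the SAP must exclude, although the ±2-week window would often have allowed a later, usable sample.

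The long-term phase exists to show whether the effect lasts, and each half-yearly visit contributes three values. Losing one removes a third of that visit's summary data, and a planned neighbouring visit may not replace it. Month 60 has no later scheduled visit.

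**Working it through.** The plan states no figure for this loss, so there is nothing to reproduce. The check compares the two rules and then bounds the loss.

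**Inputs from the documents**
- Scheduling minimum: 10 days (Table 4 footnote c; Protocol 6.2.2.3).
- Exclusion period: W = 5 × half-life (SAP 6.7.1 and 7).
- Window: ±14 days (Table 4). Subjects: 3.

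**Inputs assumed**
- Long-acting half-life: 60 to 120 h.
- On-demand long-acting infusions: 1, 2 or 4 per subject-year, occurring at random.

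**Step 1: where the rules agree.** 5 × half-life = 10 days gives 10 × 24 / 5 = 48 h. At or below 48 h, a sample at day 10 or later is kept. Above 48 h, a sample between day 10 and W meets the footnote and is excluded. At the assumed 60 to 120 h, W = 12.5 to 25 days.

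**Step 2: what the window can save.** The latest in-window visit is 14 days after the target date. The longest half-life it can clear is (14 + days from infusion to target) × 24 / 5:
- infusion 10 days before target: 24 days elapsed, up to 115 h
- infusion 5 days before: 19 days, up to 91 h
- infusion on the target date: 14 days, up to 67 h

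**Step 3: share saved.** Let u be the days from infusion to target. If sites wait only the minimum, the sample falls max(u, 10) days after the infusion and is lost when that is below W. Timing the visit to W saves it when u lies between max(0, W − 14) and W. With u uniform, the share saved is the smaller of 1 and 14 / W.

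| Half-life (assumed) | W, days | Share saved |
|---|---|---|
| 60 h | 12.5 | 100% |
| 72 h | 15.0 | 93% |
| 80 h | 16.7 | 84% |
| 96 h | 20.0 | 70% |
| 120 h | 25.0 | 56% |

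**Step 4: which visits count.** The protocol amendment of 10 Feb 2021 says that all subjects were then approaching Month 30. The SAP change-log entry that applies the 5-half-life rule to bleeding rates is dated 08 Apr 2021, and a programming note in the SAP shells refers to a Month 30 data transfer received on 14 Apr 2021. Months 18, 24 and 30 were therefore scheduled before the rule could guide them. Months 36, 42, 48, 54 and 60 remain: 5 × 3 = 15 values.

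**Step 5: bound on avoidable losses.** For W of 14 days or more, the saveable band is 14 days wide. The chance of an infusion in it is 1 − exp(−r × 14 / 365.25).
- r = 1: 3.8% per visit; × 15 = 0.6 values
- r = 2: 7.4%; × 15 = 1.1
- r = 4: 14.2%; × 15 = 2.1

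By Version 4.0, a year after the February 2021 amendment, roughly Months 42 to 60 remained: 12 values, giving about 0.5, 0.9 and 1.7.

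**The case against.** **The footnote sets a floor, not a date.** Sites may wait longer, and 6.2.2.3 aims throughout at sampling when activity is expected to be at trough. A reader might infer that every compliant sample after a long-acting product is lost. The text does not support that: with an infusion 5 days before target and a visit at +14, 19 days have passed, which clears 16.7 days (80 h). This stands, and it makes Step 5 an upper bound. A later infusion can also defeat a rescue.

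**The value is not destroyed.** A reader might infer that the data are discarded. Protocol 9.9.1 keeps all measured values in flagged listings, and SAP 6.7.1 allows by-subject plots to mark exogenous use instead of omitting the contaminated points. With three subjects and descriptive analysis, those displays matter. This also stands: the firm loss is from the summary statistics.

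**Exposure may be low.** The protocol predicts mean activity near 40% of normal, expects less on-demand use, and advises against infusions at or above 40%. No half-lives are stated. The detailed contamination entry to which SAP 6.7.1 points is not readable in the public appendix, where one entry is blacked out. If only short-acting product is used, nothing is lost. This limits the size, but long-acting use is foreseen: Protocol 5.6.3 refers to extended half-life replacement, and 6.1.2 itself requires more than 10 days for long-acting product.

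**A rescue route exists.** Additional visits may include central factor IX activity, and SAP 6.3 can assign such values. This holds only in part. The visits are discretionary, and the SAP does not say that a contaminated scheduled value counts as missing.

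**No named endpoint is affected.** The listed factor IX activity endpoints stop at Week 52, and the Week 6 and Week 52 reports used the 10-day rule. This stands. What is at stake is the description of durability.

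**Conclusion.** The mismatch is in the text and needs no outside figure: above a half-life of 48 h, a visit that satisfies Table 4 footnote c can produce a value that the SAP excludes from its summaries, leaving n = 2 of 3. SAP section 7 discloses the analysis change but leaves visit timing untouched.

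The expected loss is modest and uncertain: at most about 0.6, 1.1 or 2.1 of 15 values, on assumed half-lives of at least 67 h (slightly less below that) and assumed infusion rates.

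Two stronger readings should be resisted. One is that all 24 long-term values (8 visits × 3 subjects) could have been protected. Nine of them, at Months 18 to 30, were scheduled before the rule existed. The other is that the exclusions inflate apparent durability because they fall on subjects who bleed. That is conceivable, but nothing in the documents shows it.

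Table 3 footnote c breaks off in the readable text, so this point does not rely on it.

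**What to change.** 1. In Table 4 footnote c and Protocol 6.2.2.3 (and in Table 3, if it carries the same wording), set the scheduling trigger for long-term visits to the longer of 10 days and 5 half-lives of the product used, still as far as the ±2-week window allows. Taking the longer of the two matters. A bare 5-half-life trigger would shorten the wait for short-acting product to about 3.8 to 5 days (at an assumed 18 to 24 h), below the 10 days that sites now use.
2. Bring Protocol 9.9.1 into line with the exclusion rule that the SAP applies.
3. Add one sentence to SAP 6.3: a contaminated scheduled factor IX value counts as missing. An uncontaminated central-laboratory value from an additional visit can then be assigned to it when the window cannot clear the exclusion period.

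The cost is three wording changes, some visits later within the existing window, and an occasional additional visit. Factor IX treatment does not change; only the timing of sampling visits does.

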1 INTRODUCTION

1.1 Condition Background and Current Treatment

Congenital hemophilia B is an inherited bleeding disorder characterized by an increased bleeding tendency due to either a partial or complete deficiency of the essential blood coagulation factor IX (FIX). The deficiency is the result of mutations of the respective clotting factor genes. Hemophilia B is an X-linked, recessive condition, since it occurs almost exclusively in males. Females typically are asymptomatic carriers. The number of people with hemophilia B worldwide is approximately 30,000 and in the United States (US) alone is approximately 4,000 (World Federation of Haemophilia [WFH], 2017). Approximately 1 in 20,000 - 50,000 live male newborns has hemophilia B.

The severity of symptoms can vary and the severe forms become apparent early in life. About one-third of individuals with hemophilia B have a severe disorder characterized by functional factor IX levels that are less than 1% of normal (Kessler & Mariani, 2006). Moderate and mild hemophilia B, with 1 - 5% or 5 - <40% of normal factor IX level, respectively, are each observed in about one-third of patients (Kessler & Mariani, 2006).

Bleeding is the main symptom of the disease and usually increases when the infant becomes mobile. Mild cases may go unnoticed until later in life, when they occur in response to surgery or trauma. In severe or moderate hemophilia internal bleeding may occur anywhere, but bleeding into joints is most common (National Heart, Lung, and Blood Institute, 2013). Severe recurrent bleedings may lead to severe arthropathy, joint contractures and pseudotumors, resulting in chronic pain, disability and reduced CCI (Bolton-Maggs et al., 2003). As few as one to two bleeds can trigger progressive, irreversible joint disease (Gater et al., 2011).

The overall life expectancy in severe hemophilia is 63 years, which is about 15 years lower than general male population (Darby et al., 2007). Life expectancy in patients without liver complications (e.g., human immunodeficiency virus [HIV] or hepatitis C) can approach that of the general male population (Plug et al, 2006; Osooli et al 2017).

There is no cure for hemophilia B. The primary goals of hemophilia B therapy are the prevention of bleeding episodes, rapid and definitive treatment of bleeding episodes (breakthrough bleeds) that occur even while on a regular prophylactic regimen and provision of adequate hemostasis during surgery and emergencies. Currently, these goals are essentially met for hemophilia B subjects by intravenous (IV) injections of commercially available recombinant- or plasma-derived factor IX products, either at the time of a bleed (on-demand) or by regular infusions up to several times a week (prophylactically). The recent approvals of extended half-life factor IX products allow for reduced frequency of factor administration (once every 7 to 21 days) and maintaining a higher factor IX trough level (Taylor and Kruse-Jarres, 2016).

